3.2 Secondary Outcome Measures

3.2.a. Flavor Perception of Sparkling Water. We will use sensory testing to measure perception of sparkling beverages at the baseline and at the end of the study [30]. We will test a total of 6 levels of sweetness in the beverages so that we can observe if a shift in ideal level of sweetness occurs after consuming the unsweetened waters. The sparkling beverages will be labeled with randomized 3-digit codes. The participants will first taste an unsweetened and fully sweetened beverages (to control for order and desensitization effects) and then all samples (including replicates of the unsweetened and fully sweetened beverages) will be presented to participants in counterbalanced order. Participants will rate the samples for their sweetness using a "just about right" visual analog scale, with anchors at: -100, "Not sweet enough"; -50, "Slightly not sweet enough"; 0, "Just about right"; +50, "Slightly too sweet"; and +100 "Too sweet." Samples will also be rated for liking using a hedonic visual analog scale, with anchors at: -100, "Worst ever"; -50, "Dislike"; 0, "Neutral"; +50, "Like"; +100, "Best ever." Before and between each sample participants will rinse with water, and a 1 minute break will be enforced between each sample.

3.2.b. CVD Outcomes, Blood Triglycerides, Blood Pressure and Waist Circumference. We will assess these measures during study visits at the clinical centers at the same time and under fasting conditions as for the oral glucose tolerance testing. We will measure blood pressure after 5 minutes of rest, on the right arm in the supine position, using a sphygmomanometer with an appropriate sized cuff [31]. Plasma triglyceride concentrations (along with total, and low and high-density cholesterol) will be measured by the Indiana University School of Medicine Diabetes Center Translation Core laboratory (Indianapolis, IN), using established enzymatic colorimetric methods. Anthropometric measurements will include height, weight, body mass index, waist circumference, and sagittal abdominal diameter [32]. We will calculate BMI percentiles and Z-scores from age- and sex-specific reference values as defined by the Centers for Disease Control and Prevention (CDC) growth charts [33]..

3.3 Tertiary/Exploratory/Correlative Outcome Measures

3.3.a. Other Dietary Intake Behaviors, as well as Physical Activity and Sedentary Behaviors: Changes in dietary intake of fiber, potassium, magnesium, calcium and saturated fat, as well as in physical activity or interactions between these components may play a role in the observed effects. To create 4-day food records, we will use the TADA mobile app (34). Using linear modeling, we will assess the contribution of these factors as covariates.

4 Eligibility Criteria

4.1 Inclusion Criteria

- Male and female adolescents (age 10-21 years)
- Overweight and Obese (body mass index \geq 85 percentile for age and sex)
- High consumers of SSB, defined as >2 or more servings per day
- Family history of diabetes in a first or second degree relative OR prediabetes (i.e., evidence of either impaired glucose tolerance (HbA1c 5.7 – 6.4%, or plasma glucose between 140-199 mg/dL at 2 hours on oral glucose tolerance testing) or impaired fasting plasma glucose (\geq 100 mg/dL)) [37].

[figure not shown]
4.2 Exclusion Criteria

- Pregnancy
- Use of medications that affect glucose metabolism (such as glucocorticoid-containing medications or atypical antipsychotics). We will not exclude female participants who currently use, are planning to use, or planning to stop taking oral contraceptives.
- Syndromic obesity (such as Prader Willi, hypothalamic obesity, or Laurence-Moon-Biedl)

5.0 Study Design

The study design is a prospective observational study in adolescents who are at risk for developing T2D, to evaluate the effectiveness of sparkling water to reduce dietary intake of added sugars and thereby improve glycemia. Study data on consumption and the flavor profile of sparkling water will serve as a measure of acceptability. The study intervention will be to provide carbonated flavored sparkling water for 12 weeks to adolescents who have a usual intake of 2 or more servings of SSB per day and are at a high risk for developing type 2 diabetes. Study measures will be obtained before and after the exposure to carbonated flavored sparkling water and each participant will serve as his/her own control. To encourage the participants to substitute the carbonated flavored sparkling water, study personnel will send them weekly iMessages through the TADA app. In addition, we will monitor the participants' diet, using the TADA app, every two weeks, for 4 days. Study measurements will be obtained at baseline, before the intervention, during and at the end of the 12-week intervention.

Flow diagram for randomized, controlled trial

6.0 Enrollment/Randomization

Recruitment: We will recruit participants from the Youth Diabetes Prevention Clinic ([name] is the director) and from the community. We will also contact participants who have completed our ongoing DIG IT study and who consented that we could contact them for future studies (IU – IRB Protocol #1403986016). Clinic patients less than 18 years of age may be accompanied by parental guardians who report on the child's demographic information. A dietitian routinely interviews patients about dietary habits, including consumption of sugar sweetened beverages. The information regarding dietary intake of SSB may also be obtained from the Bright Futures Adolescent Supplemental Questionnaire, that we used in previous research [34]. In our experience, 56% of participants responded "yes" to drinking more than one SSB each day and 25% of patients reported that they consumed these beverages 3 or more times per day (35) [34]. We will advertise the study by placing flyers in physician clinics, newsletters and in public spaces (e.g., libraries). We will use a self-referral approach so that those who are interested will contact

the researchers. An informational meeting with the adolescents and their family member will be arranged where the study, procedures, and informed consent will be thoroughly described. After informed consent has been obtained, each volunteer will be asked to complete the screening questionnaire and a clinical profile will be obtained to check for general health. This recruiting plan has been used successfully for recruiting subjects in our ongoing DIG IT study (IU – IRB Protocol #1403986016).

We may use a e-newsletter at Indiana University, Purdue University, or Indiana University-Purdue University Indianapolis (IUPUI) for recruitment. The language for the newsletter is provided in the protocol submission. We may also use a study flyer, posted in public places such as libraries for recruitment. The language for the study flyer is provided in the protocol submission. We may recruit using public advertisements, the language for this included in the protocol submission.

Enrollment: We will enroll 16 participants. In order to enroll the 16 subjects, we will require 32 participants to undergo screening. Participants who are interested will sign informed consent and assent (assent subjects < 14 years of age). A study investigator will review with the participants all risks and benefits from participation in the study.

Randomization: This is a single arm protocol without randomization of study participants. All participants will be provided the sparkling water. Each participant will serve as his/her own control.

7.0 Study Procedures

1. **Description of Intervention - Exposure to Sparkling Water:** During baseline study visit 1, participants will be provided with 4 flavors of sparkling water (1 of each flavor) to sample in the 6 days prior to the beginning of the study. Each participant will be asked to choose the his/her most preferred flavor, which will be used during the 12-week intervention. The intervention will be to provide sparkling water to all participants and ask them to substitute the water in place of sugar sweetened beverages for 12 weeks. We will work with the parents/guardians to determine whether delivery or pickup of the beverages from a store is most feasible. To encourage and remind the participants to drink the sparkling water, study personnel will send iMessages through the TADA app, once a week. To assess the consumption of the sparkling drinks, as well as total dietary intake, the participants will create food records, using the TADA app, at baseline, every two weeks and at the end of the study.
2. **Baseline. Initial Visit One - Obtaining Consent and Glycemia and Dietary Measurements:** This meeting will occur at the Clinical Research Center at Indiana University-Purdue University Indianapolis (CRC IUPUI) . The research team will meet with potential subjects to explain the study and to consent/assent the subject. If consent/assent is obtained, the study physician or study nurse will place the continuing glucose monitor. The researcher will give instruction on tracking dietary intake, using the TADA tool. The consent documents may be mailed to the potential participant prior to the training meeting in order to have time to review them. The visit will take one hour of time. During this visit, participants will also be asked about any food allergies and dietary restrictions. This information will be used to select a snack (granola or breakfast bar type item) for participants to consume before the sensory test during baseline visit two and at the final study visit two. Consumption of the snack ensure the participant is not excessively hungry

before making the sensory ratings (hunger makes energy containing foods more palatable, skewing sensory ratings).

3. Placement of the Continuous Glucose Monitor: Free-living, glucose measures will be performed for 6 consecutive days using the Continuous Glucose Monitoring (CGM; FreeStyle Libre Pro System; Abbott; Abbott Park, IL [29]. The CGM will be obtained for 6 days approximately 1 week before the baseline study visit. For insertion of the CGM, a small area on the participant's arm will be cleaned and the tiny glucose sensor will be inserted just under the skin and held in place with Tegaderm tape. The sensor measures glucose every 15 sec and records an average glucose value every 15 min for up to 14 days. The instrument will be placed by a registered nurse or research assistant who has been trained by the manufacturer. The instrument will be used as indicated by the manufacturer and instructions for user safety will be followed. <https://www.freestylelibre.us/?source=provider.myfreestyle.com>
4. Instructions for the TADA system: Dietary intake will be measured for 4 days using the TADA tool. This device allows individuals to capture food images on mobile devices. Each food item is segmented, identified, and its volume is estimated by a trained professional. The energy and nutrients consumed can be determined by capturing "before" and "after" eating occasion images. Subjects will be provided with an iPhone for purposes of completing daily diaries and recording daily food intake for four consecutive days. Subjects will receive training on use of this tool as a research device, including contact information for research staff should problems with the iPhone rise. Each subject will be instructed and shown how to use the iPhone to take images and to send the images to the data center using software installed on the device. The procedure for taking images of each eating occasion involves the positioning of a marker next to foods and/or beverages to be consumed. When the subject is in a WiFi hotspot, the images are automatically sent to a secure server. The procedure for taking and sending each image is expected to take 10-15 seconds. The TADA system will provide a separate recording process for beverage consumption, where participants will be able to inform what beverage and how much they consumed. The iPhone Location Services option in the settings menu will be turned to "On." This will allow researchers to collect location-based information for increased accuracy during diet data analysis. This feature will enable investigators to identify the recipe components of foods especially when they are consumed in restaurant setting, since the corresponding restaurant will be identified by its location. All information obtained regarding location will only be used by investigators for assessing dietary behavior and will be stored in secured databases. The risks involved in these procedures are no more than what a person would encounter in everyday living. The iPhones will be provided in protective cases so that it is unlikely that they will be damaged if dropped during everyday use. Subjects will not incur any costs associated with the use of the iPhone. Subjects are encouraged to return the iPhone during the subsequent clinic visit with an incentive of a total of \$15. The subject should begin using the iPhone for recording daily food intake right away after the consent/assent/training meeting.
5. Baseline Study Visit Two: About 1 week after the CGM and diet measures are obtained, the subject will attend a clinic visit at the CRC IUPUI which is part of the Indiana Clinical and Translational Science Institute. The visit will take 3 1/2 hours of time.
6. Oral glucose tolerance test. Oral glucose tolerance testing will be performed during week 0 and week 12, at the CRC IUPUI in the morning after participants have undergone an overnight fast for 8 hours. Blood samples will be obtained at -15, 0, 15, 30, 60, 90,120

minutes, relative to ingestion of a glucose drink at a dose of 1.75 g/kg body weight (maximum 75 g glucose). The procedure will be performed by trained nurses at the Indiana Clinical and Translational Science Institute. Glucose readings are performed at each timepoint using point of care instruments.

7. Cardiometabolic outcomes: Blood samples for glucose, insulin, and blood lipid concentrations will be obtained in the morning after participants have undergone an 8 hour fast. Anthropometrical measures of obesity including height and weight, the body mass index, waist circumference, and sagittal abdominal diameter, will be obtained on weeks 0 and 12 [32]. Blood pressure will be measured after 5 minutes of rest, on the right arm in the supine position, using a sphygmomanometer with an appropriate sized cuff [31].
8. Sensory testing to measure perception of sparkling beverages. After the other measurements are complete, but before the sensory tests, participants will be provided a snack (granola or breakfast bar) in order to alleviate hunger. Sensory tests for will be administered at the baseline and at the end of the study. The sparkling beverages, with and without sugar, will be labeled with randomized 3-digit codes, and presented to participants in counterbalanced order. Participants will rate the samples for their sweetness using a “just about right” visual analog scale, with anchors at: -100, “Not sweet enough”; -50, “Slightly not sweet enough”; 0, “Just about right”; +50, “Slightly too sweet”; and +100 “Too sweet.” Samples will also be rated for liking using a hedonic visual analog scale, with anchors at: -100, “Worst ever”; -50, “Dislike”; 0, “Neutral”; +50, “Like”; +100, “Best ever.” Before and between each sample participants will rinse with water, and a 1-minute break will be enforced between each sample.
9. Final Study Clinic Visit One: At the end of week 11 and start of week 12, the participant and family member will attend a visit at the CRC IUPUI where the study team will obtain CGM and TADA measures. This visit will be a repeat of Baseline Study Visit 1. The visit will take 1 hour of time.
10. Final Study Clinic Visit Two: At the end of the 12 week study, we will assess the study outcomes during a clinic visit, identical to the baseline study visit 2. We will perform oral glucose tolerance testing, cardiometabolic outcomes, and flavor perception of the sparkling waters. The visit will take 3 1/2 hours of time.

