(CGM; FreeStyle Libre Pro System; Abbott; Abbott Park, IL[29]. The CGM will be administered to participants 6 days before the start of Week 0 and Week 12, and the monitor will be removed at the clinic visit. For the placement of the CGM, the back of the participant's upper arm will be cleaned with an alcohol wipe and dried. The sensor will be firmly adhered to the arm with the needle application inserted. The FreeStyle sensor measures glucose every 15 sec and records an average glucose value every 15 min for up to 14 days.

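### In-person participants receive sparkling water before baseline is complete: Day 0 sensory ratings follow product contact, and conflicting timing leaves any overlap with baseline CGM and the food record undetermined

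*Protocol*

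**What the plan says.** Product hand-out. Protocol 7.0 item 1, headed "Description of Intervention - Exposure to Sparkling Water", says that at Baseline Visit One "participants will be provided with 4 flavors of sparkling water (1 of each flavor) to sample in the 6 days prior to the beginning" (before study start). The purpose is to let each participant pick the flavor used for the 12 weeks.

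Baseline measures. Under 7.0 item 2 the CGM is placed at the same Visit One. For the diet record, item 4 says "The subject should begin using the iPhone for recording daily food intake right away after the consent/assent/training meeting", and the record runs for four consecutive days. Items 2 and 8 and the 8.0 calendar put the first in-person sensory test at Baseline Visit Two, Day 0. The only other sensory test is at the end of the study.

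Design. Section 5.0 says "Study measures will be obtained before and after the exposure to carbonated flavored sparkling water" and, later in the same section, "Study measurements will be obtained at baseline, before the intervention, during and at the end of the 12-week intervention". Section 6.0 describes a single arm: "Each participant will serve as his/her own control". The SAP models the sensory ratings on concentration, time and their interaction, with Pre and Post defined relative to the 12-week intervention. It is written in the past tense.

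Timing of Visit One and the baseline measures:
- Protocol 3.1.d: "The CGM will be administered to participants 6 days before the start of Week 0 and Week 12", with removal at the clinic visit.
- Protocol 7.0 item 3: "The CGM will be obtained for 6 days approximately 1 week before the baseline study visit".
- Protocol 7.0 item 5: Visit Two comes roughly a week after the CGM and diet measures.
- Protocol 8.0: Visit One at -2 weeks, Visit Two at Day 0, each allowed to vary by 7 days either way.

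Remote alternative (16.2): the flavor is chosen in Session 1, and no take-home sampling is described.

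**The concern.** With one arm and no randomization, the baseline measurement is the whole control condition. Handing out the study product before that baseline is complete can blur the contrast the trial is meant to measure.

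Three measures are involved. The secondary objective asks whether acceptance of the drinks improves after 12 weeks, and for in-person participants the Day 0 ratings come after they have had the drinks at home. CGM and dietary intake are both listed as primary outcomes. If sampling falls inside their baseline windows and a sample replaces a sugar-sweetened beverage (SSB) one for one, recorded baseline SSB intake falls and the measured diet change shrinks. If the samples are drunk in addition to the usual SSBs, that effect does not arise. For the sensory ratings, neither the size nor the direction of any shift can be read from the documents.

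**Working it through.** The plan gives no figure for this, so the check is one of sequence and overlap.

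**Step 1: sensory ratings.** Hand-out is at Visit One (7.0 item 1). The first in-person test is at Visit Two (7.0 items 2 and 8; 8.0). No rating is planned before the hand-out. The order is therefore hand-out, sampling, Day 0 rating, whichever statement of Visit One timing is used.

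**Step 2: overlap with CGM and food record.** Let Day 0 be Visit Two and v the day of Visit One. Two assumptions are needed: the beginning of the study means Day 0, and no sample is opened before day -6.
- Sampling days: -6 to -1 (six days, 7.0 item 1).
- CGM days: v to v+5 (six days, 3.1.d and 7.0 item 3).
- Record days: v to v+3 (four days starting at once, 7.0 item 4).
- CGM overlap = number of days from max(v, -6) to v+5. Record overlap = number of days from max(v, -6) to v+3. Either is zero if its range is empty.

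| v | CGM days overlapping (of 6) | Record days overlapping (of 4) |
|---|---|---|
| -14, -13, -12 | 0 | 0 |
| -11 | 1 | 0 |
| -10 | 2 | 0 |
| -9 | 3 | 1 |
| -8 | 4 | 2 |
| -7 | 5 | 3 |
| -6 | 6 | 4 |

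For example, at v = -7 the CGM days are -7 to -2, of which -6 to -2 (five) fall in the sampling window; the record days are -7 to -4, of which -6 to -4 (three) do.

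**Step 3: what each statement implies.**
- 3.1.d: v = -6, so 6 of 6 and 4 of 4.
- 7.0 item 3: placement about a week before gives v = -7, so 5 of 6 and 3 of 4. Six days completed about a week before gives v = -13, so none.
- 7.0 item 5: open to the same two readings, because obtaining the measures can mean placing the device or finishing the recording. Item 9 uses that verb for the final visit that repeats Visit One.
- 8.0: v = -14, so none. Overlap with CGM begins if Visit One is 3 days late (-11) and with the record if it is 5 days late (-9). Both lie inside the 7-day allowance, whose late edge (-7) gives 5 of 6 and 3 of 4.

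**Step 4: relax the assumption on opening.** Participants hold the drinks from Visit One. If they start on them at hand-out, every CGM and record day can fall after first contact, so overlap can be 6 of 6 and 4 of 4 for any v.

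**The case against.** Several counter-arguments are sound.

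- *Exposure means the 12 weeks.* A reader might infer that 5.0 promises measurement before any contact and that 7.0 breaks the promise. But the sentence in 5.0 follows directly on a description of the 12-week provision, the same section later speaks of baseline before the intervention, and the SAP defines Pre in the same way. On that reading Day 0 is a valid baseline. This stands.
- *No product-naive baseline was promised.* The hypothesis in 2.2 concerns 12 weeks of drinking, 1.0 says such waters are commercially available, 4.1 and 4.2 exclude no prior users, and 3.2.a opens each test with an unsweetened taste. This stands too. The in-session taste, however, is part of both tests, whereas the take-home samples are an extra, unstandardized contact before the first.
- *The dose of contact is small.* At an assumed two drinks a day, four drinks are 4 / (2 x 84) = 4 / 168 = 2.4% of the 12-week volume. That argues against a large effect, though a share of volume does not show when ratings begin to move.
- *Any displacement of SSBs is conservative, and the beverage record would show it.* The first part is right for the diet change but does not settle the sensory direction. The second holds only for the four recorded days.
- *It may concern nobody analyzed.* 16.2 moves sensory testing online, and the SAP does not say which procedure was used. This stands, and is why the number tested in person has to be reported.
- *Home sampling has a purpose.* It does, but 16.2 shows that a flavor can be chosen without it.

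**Conclusion.** The point holds as avoidable contamination of an in-person baseline that is the only comparator, together with a baseline calendar that does not agree with itself. In-person Day 0 sensory ratings follow the product hand-out under every timing reading. Overlap of sampling with baseline CGM and the food record is undetermined, from none to complete.

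The size is limited: at most four drinks per participant, and an effect that may be zero. One-for-one replacement of SSBs inside the record window would understate the diet change; the direction for sensory ratings is unknown.

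Three stronger inferences are not supported. The documents do not show that CGM and diet baselines were contaminated, since two statements can be read either way and the calendar's scheduled date gives no overlap under the assumptions above. Nor does that date rule overlap out: it does so only if no sample is opened before day -6 and the study begins at Day 0. And nothing here touches the 2-hour glucose sample size in 12.0 or the remote procedure in 16.2; no effect on glucose is claimed.

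**What to change.** Reconcile 3.1.d, 7.0 items 1 to 3 and 5, and the 8.0 calendar into one baseline calendar that fixes the order of CGM, food record, hand-out and Day 0, and define the beginning of the study.

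For any participants still to be enrolled, give out no product until CGM, food record, OGTT and sensory testing are complete at Baseline Visit Two. Have the flavor chosen at the end of that visit, or without take-home sampling as in 16.2 Session 1, so that the 12-week start is not delayed. If the in-person sensory test uses the participant's own flavor, the second route applies.

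For participants already measured, report how many were tested in person and how many received samples before baseline measures, and state as a limitation that their baseline may not be free of product contact. Do not repair this with an analysis that omits baseline days on which sparkling water was recorded: sparkling water intake is part of primary outcome 3.1.a, so that would select on the outcome.

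The cost is small: the visits and product stay the same, and only wording and the calendar change. The drawback is a flavor chosen without home tasting. If a take-home period is kept after Visit Two, the 12-week clock and the two-weekly records must start after it; otherwise a six-day period would use up 6 of the 84 intervention days.

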8.0 Study Calendar

STUDY PROCEDURES	Baseline Study Visit One	Baseline Study Visit Two	Follow-up					Final Study Visit One	Final Study Visit Two
	-2 wk	Day 0	2 wk	4 wk	6 wk	8 wk	10 wk	11 wk	Week 12
Consent/Accent	X								
CGM monitoring	X							X	
TADA Dietary Assessment	X		X	X	X	X	X	X	
Oral Glucose Tolerance Testing		X							X

Cardiometabolic outcomes		X							X
Sensory Testing		X							X

To allow for deviations in terms of timing and scheduling of study visits, we will consider variations of +/- 7 days from the scheduled visit.

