16.2 Study Procedures

The study procedures would be conducted in three different online sessions. The purpose of the online sessions is to ensure participants and their parents/guardians have full understanding of the study and perform the tasks as instructed, minimizing any potential risks and maximizing accuracy of results. Each online session would have up to 1 hour in duration. Details for each session are noted below.

Session 1

- 1. Consent/Accent forms.** Consent/assent forms will be mailed to potential participants. During the online session, a study investigator will review with participants and their parent/guardians all the risks and benefits of participating in the study. Upon decision of participating in the study, participants older than 14 years of age will sign the consent forms, and participants younger than 14 years will have their parents/guardians sign the assent forms. If participants consent/assent, they will sign the forms, send immediate pictures of the signature pages, and then return to us physically using a provided stamped envelope for return. If a participant does not consent/assent, we will end the session.
- 2. TADA instructions.** The TADA app will be previously installed on the iPhones provided to participants. After consent/assent, participants will be instructed on how to use the app to report their consumption of flavored seltzer water and other beverages, as well as how to take pictures of their food for the 4-day food record (every 2 weeks).
- 3. Anthropometric measurements.** Participants will be asked to weigh themselves and measure their height with the help of another person. They will also be guided on how to measure their waist circumference, as previously described (38). If participants do not have a scale or measuring tape, these items will be delivered to participants' houses.
- 4. Choosing seltzer water and soda flavors for sensory tests and 12-week intervention.** Participants will be given the option of choosing flavored sparkling water. Sugar-sweetened soda of the matching flavor will be used in the sensory tests.

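### Food records start on whatever weekday the visit falls, so weekend days need not match between rounds; this adds avoidable error to individual changes in sugar-sweetened beverage (SSB) intake.

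*Protocol*

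**What the plan says.** SSB and sparkling water intake is listed as a primary outcome (Protocol section 3.1.a), and each participant is his or her own control (sections 5.0 and 6.0).

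Section 7.0, item 4 defines a record as "recording daily food intake for four consecutive days" and fixes the baseline start: "The subject should begin using the iPhone for recording daily food intake right away after the consent/assent/training meeting". Section 5.0 repeats the measurement "using the TADA app, every two weeks, for 4 days". The remote plan in section 16.2 keeps the same four-day, two-weekly pattern.

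The last record is tied to Final Study Clinic Visit One (section 7.0, item 9), timed "At the end of week 11 and start of week 12", and "This visit will be a repeat of Baseline Study Visit 1". The study calendar (section 8.0) shows dietary rounds at -2, 2, 4, 6, 8, 10 and 11 weeks. On timing it adds that "we will consider variations of +/- 7 days from the scheduled visit".

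Neither document names a weekday, requires a weekend day, matches weekdays across a participant's rounds, or weights or adjusts for day of the week. The covariates in section 3.3.a are nutrients and physical activity. Section 12.0 names no test for SSB intake and does not say how the rounds are combined. The SAP models sensory ratings only.

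**The concern.** Four consecutive days are too few to average over the week, so the start day decides how much of the weekend is sampled. If adolescents drink different amounts of SSB on weekend days and weekdays, a participant whose baseline and later records hold different numbers of weekend days will show a change in SSB intake without any change in behaviour.

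This matters most where each person's own change is used. The primary hypothesis (section 2.1) contrasts participants who reduce SSB with those who do not, and section 12.0 plans to relate SSB change to changes in taste perception and glycemia. Error in the individual change can put people on the wrong side of the first comparison and weaken the second. With 13 to 16 participants and no control group, there is little room to absorb it.

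**Working it through.** **The plan's own figure.** The plan gives no figure for day-of-week variation. Its only design figure is 13 evaluable participants, based on 2-hour glucose (section 12.0). The difference is 143.9 − 123.7 = 20.2 mg/dL. The before-after correlation r is not stated. With r = 0.1 assumed, the SD of the change is √(9.6² + 22.6² − 2 × 0.1 × 9.6 × 22.6) = 23.65, and a two-sided 5% paired t-test has 80.7% power at n = 13. At r = 0 it needs 14. The figure reproduces and does not depend on SSB intake. It is used below only as the group size.

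**Weekend days k in four consecutive days** (Saturday and Sunday counted as weekend):

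| Start | Mon | Tue | Wed | Thu | Fri | Sat | Sun |
|---|---|---|---|---|---|---|---|
| k | 0 | 0 | 1 | 2 | 2 | 2 | 1 |

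For Monday-to-Friday visits the range is still 0 to 2, whether recording starts the same day (0, 0, 1, 2, 2) or the next day (0, 1, 2, 2, 2).

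**Does the schedule match weekdays?** From -2 weeks to 11 weeks is 13 × 7 = 91 days, a multiple of 7, so an exactly kept calendar repeats the weekday. With each visit free to move by up to 7 days either way, every weekday offset from 0 to 6 is possible.

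**Size of the artefact.** Let d be weekend minus weekday intake in servings per day (assumed; neither its size nor its sign is in the documents), and D the difference in k between two records. The artefact in the change in mean daily intake is (D/4) × d. Since |D| is at most 2, its maximum is d/2.

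If the two start days are independent, Var(D) = 2 × Var(k):

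| Start days | Var(k) | SD(D)/4 | P(D ≠ 0) | P(full 2-day difference) |
|---|---|---|---|---|
| Any day | 0.694 | 0.295 | 65% | 24% |
| Mon–Fri, same-day start | 0.80 | 0.316 | 64% | 32% |
| Mon–Fri visit, next-day start | 0.64 | 0.283 | 56% | 24% |

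The SD for one participant is therefore about 0.28 to 0.32 × d. For the mean of 13, divide by √13 = 3.606, which gives about 0.08 to 0.09 × d. In servings per day, for the same-day Monday-to-Friday case:

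| Assumed d | Maximum, one person | SD, one person | SD, mean of 13 |
|---|---|---|---|
| 0.25 | 0.125 | 0.079 | 0.022 |
| 0.5 | 0.25 | 0.158 | 0.044 |
| 1.0 | 0.50 | 0.316 | 0.088 |
| 2.0 | 1.00 | 0.632 | 0.175 |

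If d = 0 there is no artefact.

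**If the six later rounds were averaged** and their start days were independent, the variance would fall from 2v to v + v/6, where v is the variance from one record. The SD would be multiplied by √(7/12) = 0.76, so about 0.22 to 0.24 × d per person. The baseline part remains.

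**The case against.** The strongest reply is that the plan nearly matches weekdays already. Dietary rounds are whole weeks apart. The final record, like the baseline one, starts from a clinic visit, and that visit is described as a repeat of the baseline visit. Section 3.1.d, which places the glucose monitor 6 days before Week 0 and Week 12, also implies a gap of 84 days, again a multiple of 7. Independent start days are therefore a pessimistic assumption. This stands. Still, the match is a by-product of the calendar that the permitted window can undo, and nothing sets the start day at weeks 2 to 10.

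A reader might infer a stronger point: that habitual clinic weekdays push the imbalance the same way in most participants and so bias the group's before-after change. The documents do not support this. Habitual weekdays at both visits would tend to give similar weekend counts at baseline and at the end, so the artefact would largely cancel. Bias in the mean needs a systematic shift in weekday between baseline and the later records, and no section shows one. It could arise if clinic-anchored baselines were set against the rounds without visits, but the plan does not say which rounds form the after value.

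A reader might also take the worst case as the effect. At d = 1 the maximum of 0.50 is 25% of the 2-servings entry level (section 4.1). That applies only to a participant who moves between no weekend day and two. The SD for the mean of 13 is about 0.09, or 4% of that level.

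**Conclusion.** The gap is real and minor. Day-of-week matching rests on the calendar being kept exactly, and the plan has no rule to secure it and no adjustment for when it fails. The consequence is extra error in individual SSB changes, not a demonstrated bias in the group mean. The size depends on d, which is assumed here, and the SDs assume independent start days. Closer matching in practice would make them smaller. The sample size and the 2-hour glucose comparison are unaffected.

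**What to change.** In section 7.0, item 4, replace the immediate start with this rule: each participant records on the same four weekdays in every round, including at least one weekend day. Apply it to weeks 2 to 10 and to the remote plan, and book Baseline Study Visit One and Final Study Clinic Visit One on the same weekday where possible. D is then 0 for everyone, and the day-of-week part of the change is zero for any d.

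The cost is wording and scheduling. Only Monday and Tuesday starts need to move, by at most two days, to Wednesday. Two days plus four recording days is six, which fits the interval of about one week before Baseline Study Visit Two.

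The SAP describes its models as already run, so some or all records may exist. For those, report the weekend-day count per participant and round, and adjust the SSB change for the difference in count. State also which rounds form the after value.

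Weighting weekdays and weekend days 5:2 is optional. It is not needed for the before-after change once weekdays match, and it cannot repair a record with no weekend day.
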